8.3.5 Pregnancy Testing

Female subjects of childbearing potential will be tested for serum and/or urine β -hCG at specific timepoints outlined in the SoA. In the case of a positive or borderline serum β -hCG pregnancy test at the pre-trial (screening) visit, the subject must not enter the trial; in the case of a positive or borderline urine β -hCG pregnancy test during the trial, a serum β -hCG pregnancy test will be required. If the pregnancy has been confirmed the subject must be discontinued from the trial immediately and the pregnancy must be reported to the Sponsor as outlined in Section 8.4.5.

8.3.6 Clinical Safety Laboratory Assessments

- Refer to Appendix 2 for the list of clinical laboratory tests to be performed and to the SoA for the timing and frequency.

- The investigator or medically qualified designee (consistent with local requirements) must review the laboratory report, document this review, and record any clinically relevant changes occurring during the study in the AE section of the case report form (CRF). The laboratory reports must be filed with the source documents. Clinically significant abnormal laboratory findings are those which are not associated with the underlying disease, unless judged by the investigator to be more severe than expected for the participant's condition.
- All protocol-required laboratory assessments, as defined in Appendix 2, must be conducted in accordance with the procedures manual and the SoA.
- If laboratory values from nonprotocol specified laboratory assessments performed at the institution's local laboratory require a change in study participant management or are considered clinically significant by the investigator (eg, SAE or AE or dose modification), then the results must be recorded in the appropriate CRF (eg, SLAB).
- For any laboratory tests with values considered clinically significantly abnormal during participation in the study or within 14 days after the last dose of study intervention, every attempt should be made to perform repeat assessments until the values return to normal or baseline or if a new baseline is established as determined by the investigator.

8.3.7 Suicidal Ideation and Behavior Monitoring

8.3.7.1 Clinical Assessments for Suicidal Ideation and Behavior Monitoring

Suicidal ideation and behavior will be prospectively assessed during this study using the C-SSRS. The C-SSRS should be administered by trained raters at the time points indicated in the SoA. In addition, C-SSRS will be administered at any unscheduled visit where safety assessments are performed. The C-SSRS will not be routinely administered at visits with a sole purpose of PK sampling and/or witnessed study intervention administration. Site staff should review the contents of the C-SSRS for completeness. If the C-SSRS is administered by someone other than the investigator, consider providing the completed C-SSRS to the investigator for review, prior to their assessment of the participant and to further inform their evaluation. The C-SSRS is not explicit about whether the participant specifically has ideation at the time of screening. If a participant reports a prior history of ideation/behavior at screening, the assessor should also inquire and document if this is also present at the time of the screening visit.

Participants who at any time during this study report suicidal ideation or behavior that is considered to be an adverse event, either between visits or during visit interviews, must be assessed by the Investigator. Participants who report suicidal ideation with intent, with or without a plan or method (i.e., a positive response to items 4 or 5 in the assessment of suicidal ideation on the C-SSRS) or suicidal behavior must be evaluated that day by a psychiatrist or other trained mental health professional who is a licensed psychologist, social worker or mental health nurse practitioner (or comparable professional qualification in countries outside of the United States). Only participants whose suicidal ideation is passive, who expressly deny any intent to act, and who, after evaluation, are not judged to be at

serious risk for self-harm during the course of the study may continue in the study; others must be discontinued from study participation and receive appropriate clinical follow-up care to ensure their safety. In addition, all AEs of suicidal ideation or behavior must be recorded as an Event of Clinical Interest (see Section 8.4.7). Sites are to designate which health care professionals are to be responsible for acute care on-site and to specify referral center(s) to be used for further evaluation.

8.3.8 Monitoring for Extrapyrarnidal Symptoms

The investigator or qualified designee will complete the BARS, AIMS and SAS at times specified in the SoA. Additional assessments at unscheduled times outside of the SoA will be conducted by study staff if it is observed or a participant reports complaints of dystonia and or akathisia.

8.3.9 Assessment of Neuropsychological Effects

For the assessment of the psychological effects, all participants will complete the VAS at times specified in SoA. Prior to the initial administration of the VAS participants will be trained by study staff and will practice the assessment.

In addition, participants with schizophrenia will also complete the BPRS at times specified in SoA.

A General Neurological Exam will be performed at the Screening and Baseline visits for all participants. A targeted Neurological Exam will be administered at times specified in the SoA. Details of the neurological examinations are in Appendix 11 and Appendix 12.

8.4 Adverse Events (AEs), Serious Adverse Events (SAEs), and Other Reportable Safety Events

The definitions of an AE or SAE, as well as the method of recording, evaluating, and assessing causality of AE and SAE and the procedures for completing and transmitting AE, SAE, and other reportable safety event reports can be found in Appendix 3.

Adverse events, SAEs, and other reportable safety events will be reported by the participant (or, when appropriate, by a caregiver, surrogate, or the participant's legally authorized representative).

The investigator and any designees are responsible for detecting, documenting, and reporting events that meet the definition of an AE or SAE as well as other reportable safety events. Investigators remain responsible for following up AE, SAEs, and other reportable safety events for outcome according to Section 8.4.3.

The investigator, who is a qualified physician, will assess events that meet the definition of an AE or SAE as well as other reportable safety events with respect to seriousness, intensity/toxicity and causality.

8.4.1 Time Period and Frequency for Collecting AE, SAE, and Other Reportable Safety Event Information

All AEs, SAEs, and other reportable safety events that occur after the consent form is signed but before treatment allocation/randomization, must be reported by the investigator for randomized participants only if the event is the result of a protocol-specified intervention, including but not limited to washout or discontinuation of usual therapy, diet, placebo treatment, or a procedure.

From the time of treatment allocation/randomization through 14 days following cessation of treatment, all AEs, SAEs and other reportable safety events must be reported by the investigator.

Additionally, any SAE brought to the attention of an investigator any time outside of the time period specified in the previous paragraph also must be reported immediately to the Sponsor if the event is considered drug-related.

Investigators are not obligated to actively seek AE or SAE or other reportable safety events in former study participants. However, if the investigator learns of any SAE, including a death, at any time after a participant has been discharged from the study, and he/she considers the event to be reasonably related to the study intervention or study participation, the investigator must promptly notify the Sponsor.

All initial and follow-up AEs, SAEs, and other reportable safety events will be recorded and reported to the Sponsor or designee within the time frames as indicated in [Table 5](#).

Table 5 Reporting Time Periods and Time Frames for Adverse Events and Other Reportable Safety Events

Type of Event	Reporting Time Period: Consent to Randomization/ Allocation	Reporting Time Period: Randomization/ Allocation through Protocol-Specified Follow-up Period	Reporting Time Period: After the Protocol Specified Follow-up Period	Timeframe to Report Event and Follow-up Information to SPONSOR:
Non-Serious Adverse Event (NSAE)	Report if: - due to protocol-specified intervention - causes exclusion - participant is receiving placebo run-in or other run-in treatment	Report all	Not required	Per data entry guidelines
Serious Adverse Event (SAE) including Cancer and Overdose	Report if: - due to protocol-specified intervention - causes exclusion - participant is receiving placebo run-in or other run-in treatment	Report all	Report if: - drug/vaccine related. (Follow ongoing to outcome)	Within 24 hours of learning of event
Pregnancy/Lactation Exposure	Report if: - due to intervention - causes exclusion	Report all	Previously reported – Follow to completion/termination; report outcome	Within 24 hours of learning of event
Event of Clinical Interest (require regulatory reporting)	Report if: - due to intervention - causes exclusion	Report - Potential DILI - Require regulatory reporting	Not required	Within 24 hours of learning of event
Event of Clinical Interest (Do not require regulatory reporting)	Report if: - due to intervention - causes exclusion	Report - non-DILI ECIs and those not requiring regulatory reporting	Not required	Within 5 calendar days of learning of event

8.4.2 Method of Detecting AEs, SAEs, and Other Reportable Safety Events

Care will be taken not to introduce bias when detecting AEs and/or SAEs and other reportable safety events. Open-ended and nonleading verbal questioning of the participant is the preferred method to inquire about AE occurrence.

8.4.3 Follow-up of AE, SAE, and Other Reportable Safety Event Information

After the initial AE/SAE report, the investigator is required to proactively follow each participant at subsequent visits/contacts. All AE, SAE, and other reportable safety events including pregnancy and exposure during breastfeeding, events of clinical interest (ECI), cancer, and overdose will be followed until resolution, stabilization, until the event is otherwise explained, or the participant is lost to follow-up (as defined in Section 7.3). In addition, the investigator will make every attempt to follow all nonserious AEs that occur in randomized participants for outcome. Further information on follow-up procedures is given in Appendix 3.

8.4.4 Regulatory Reporting Requirements for SAE

Prompt notification (within 24 hours) by the investigator to the Sponsor of SAE is essential so that legal obligations and ethical responsibilities towards the safety of participants and the safety of a study intervention under clinical investigation are met.

The Sponsor has a legal responsibility to notify both the local regulatory authority and other regulatory agencies about the safety of a study intervention under clinical investigation. All AEs will be reported to regulatory authorities, IRB/IECs, and investigators in accordance with all applicable global laws and regulations (ie, per ICH Topic E6 (R2) Guidelines for Good Clinical Practice [GCP]).

Investigator safety reports must be prepared for suspected unexpected serious adverse reactions (SUSARs) according to local regulatory requirements and Sponsor policy and forwarded to investigators as necessary.

An investigator who receives an investigator safety report describing an SAE or other specific safety information (eg, summary or listing of SAE) from the Sponsor will file it along with the IB and will notify the IRB/IEC, if appropriate according to local requirements.

8.4.5 Pregnancy and Exposure During Breastfeeding

Although pregnancy and infant exposure during breastfeeding are not considered AEs, any pregnancy or infant exposure during breastfeeding in a participant (spontaneously reported to the investigator or their designee) that occurs during the study are reportable to the Sponsor.

All reported pregnancies must be followed to the completion/termination of the pregnancy. Pregnancy outcomes of spontaneous abortion, missed abortion, benign hydatidiform mole, blighted ovum, fetal death, intrauterine death, miscarriage, and stillbirth must be reported as

serious events (Important Medical Events). If the pregnancy continues to term, the outcome (health of infant) must also be reported.

8.4.6 Disease-related Events and/or Disease-related Outcomes Not Qualifying as AEs or SAEs

Disease-related Events and/or Disease-related Outcomes Not Qualifying as AEs or SAEs are not applicable to this study.

8.4.7 Events of Clinical Interest (ECIs)

Selected nonserious and SAEs are also known as ECIs and must be reported to the Sponsor.

Events of clinical interest for this study include:

1. An overdose of Sponsor's product, as defined in Section 8.5, that is not associated with clinical symptoms or abnormal laboratory results.
2. An elevated AST or ALT lab value that is greater than or equal to 3X the upper limit of normal and an elevated total bilirubin lab value that is greater than or equal to 2X the upper limit of normal and, at the same time, an alkaline phosphatase lab value that is less than 2X the upper limit of normal, as determined by way of protocol-specified laboratory testing or unscheduled laboratory testing.*

*Note: These criteria are based upon available regulatory guidance documents. The purpose of the criteria is to specify a threshold of abnormal hepatic tests that must trigger an additional evaluation for an underlying etiology. The study site guidance for assessment and follow up of these criteria can be found in the Investigator Study File Binder (or equivalent).

It may also be appropriate to conduct additional evaluation for an underlying etiology in the setting of abnormalities of liver blood tests including AST, ALT, bilirubin, and alkaline phosphatase that do not meet the criteria noted above. In these cases, the decision to proceed with additional evaluation will be made through consultation between the study investigators and the Sponsor Clinical Director. However, abnormalities of liver blood tests that do not meet the criteria noted above are not ECIs for this study.

3. Suicidal ideation and/or suicidal behavior as reported in the C-SSRS scores, TEAEs or any self-injurious behavior
4. Dystonia
5. New or worsening tardive dyskinesia
6. QTcF interval of ≥ 500 msec (the average of the three QTcFs will be used)

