- a. Meals should be given at approximately the same time every day starting on Day -1 (time-matched to postdose meals) through Day 20. Breakfast will be given at ~1 hour postdose, lunch given at ~4 hours postdose, a snack given at ~8 hours postdose and dinner at ~12 hours postdose. All meals will follow the completion of all specified procedures at that timepoint.
- b. Panel A will be confined minimally from Day -2 through Day 21. Panel B will be confined within a week of starting their antipsychotic washout period through Day 21; minimally subjects will be confined from Day -6 through Day 21. Panel C will be confined minimally from Day -1 through Day 21.
- c. Single HR and BP measurements will be obtained at all postdose timepoints. On the following days, specific timepoints are noted:
- Day -1: Triplicate measurements time- matched to 8 hour post dose vital sign
 - Day 2 and Day 5: 8 hours post-dose (Panel A only)
 - Day 8, Day 11, Day 14 and Day 17: 8 hours post-dose
 - Day 10, Day 12, Day 13, Day 15, Day 16 and Day 18: 10 and 16 hours postdose
- d. Orthostatic assessments in HR and BP will follow semi recumbent vital sign assessments. Subjects should be standing for approximately 3 minutes prior to the orthostatic assessments. Orthostatic HR and BP measurements will be obtained on:
- Day -1: Time- matched to 8 hour post dose orthostatic vital sign.
 - Day 2 and Day 5: 8 hours post-dose (Panel A only).
 - Day 8, Day 11, Day 14 and Day 17: 8 hours post-dose
 - Day 10, Day 12, Day 13, Day 15, Day 16 and Day 18: 10 and 16 hours postdose
- e. For Panels A and B, single 12-lead safety ECG measurements will be at all postdose timepoints. On the following days, specific timepoints are noted:
- Day 1: Triplicate measurements within 2 hours prior to dosing.
 - Day 2 and Day 5: 8 hours post-dose (Panel A only).
 - Day 8, Day 11, Day 14 and Day 17: 8, 10 and 16 hours post-dose
- f. For Panels A and B, continuous (24-hour) Holter ECG measurements will be performed from approximately 30 minutes prior to dose administration and until 24 hours post-dose. ECG data will be extracted on:
- Day -1 (baseline measurement): time matched to dosing days at the following timepoints: 2, 6, 8, 10, 12, 16 and 24 hours
 - Day 7, Day 10, Day 13 and Day 16: predose, 2, 6, 8, 10, 12, 16 and 24 hours post-dose.
 - Day 18: 2, 6, 8, 10, 12, 16, 24, 36 and 48 hours post-dose.

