6.6 Dose Modification (Escalation/Titration/Other)

All dose titration decisions will be made jointly by the investigator and the Sponsor. Each dose titration decision for each individual participant will occur after 3 days of dosing per dose level.

Dose titration decisions for each participant will be based on available (as per the SoA) safety variables: VS, 12-lead safety ECG, laboratory safety tests, AEs, C-SSRS, BPRS, and EPS evaluations from the previous dose levels. Pharmacokinetic and pharmacodynamic data may be included in the dose titration decisions.

If, as judged by the Sponsor and investigator, the safety and tolerability data do not justify dose titration, the dose will not be increased as planned. Instead, participants may:

- Skip a single dose and dosing may continue at the same dose level or adjusted downwards
- Receive the same dose level to further explore safety and tolerability at that level
- Receive a lower dose of the study intervention

- Dosing may be stopped

If appropriate medical care necessitates dosing to be stopped or a lower dose given, the investigator may do so without consultation with the Sponsor.

Participant discontinuation criteria are outlined in Section 7.

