8.3.4 Electrocardiograms

12-Lead Safety Electrocardiogram

Special care must be taken for proper lead placement by qualified personnel. Skin should be clean and dry prior to lead placement. Participants may need to be shaved to ensure proper lead placement. Female participants may need to remove interfering garments.

Participants should be resting in the semi-recumbent for at least 10 minutes prior to each ECG measurement.

The correction formula to be used for QTc is Fridericia.

If repeat ECGs are required, the clinical site will decide whether to leave the electrodes in place or mark the position of the electrodes for subsequent ECGs. To mark the position of the electrodes, 12-lead electrode sites will be marked on the skin of each participant with an ECG skin marker pen to ensure reproducible electrode placement.

In all Panels, baseline (prior to Day 1 dosing) ECGs will be obtained in triplicate at least 1-2 minutes apart as per the SoA. The mean of these measurements will be used as the baseline to calculate change from baseline for safety evaluations (and for rechecks, if needed).

In Panels A, B and D, postdose ECG measurements will be single measurements. In Panel C, postdose ECG measurements will be obtained in triplicate at least 1-2 minutes apart as per the SoA.

During each treatment period, if a participant demonstrates an increase in QTc interval ≥ 60 msec compared with mean predose baseline measurement, the ECG will be repeated twice within 10 minutes (applies to Panels A, B and D only as Panel C will have triplicate post dose ECG evaluations). The mean value of the QTc interval from the 3 ECGs will represent the value at that time point. If the mean QTc interval increase from baseline for any postdose time point is ≥ 60 msec, the participant will continue to be monitored by repeat 12-lead ECGs every 15 minutes for at least 1 hour or until the QTc is within 60 msec of baseline. If prolongation of the QTc interval ≥ 60 msec persists, a consultation with a study cardiologist may be appropriate and the Sponsor should be notified.

If the mean QTc interval is ≥ 500 msec, the Sponsor should be notified, and the ECGs should be reviewed by a cardiologist. The participant should be telemetry-monitored (until the QTc is < 500 msec) or should be considered for transfer to a location where closer monitoring and definitive care (e.g., a cardiac or intensive care unit) is available.

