If the participant has unstable hemodynamics, or has any clinically significant dysrhythmias noted on telemetry, the participant should be immediately transferred to an acute care setting for definitive therapy.

If prolongation of the QTc is noted, concomitant medications that prolong QTc should be held until the QTc is within 60 msec of baseline and the QTc is <500 msec.

A study cardiologist will be consulted by the Principal Investigator as needed to review ECG tracings with abnormalities.

24-Hour Holter Assessment (Panel A ,Panel B and Panel D only)

For the entire 24-hour Holter recording duration, participants should not wear metal jewelry such as watches, necklaces, and/or bracelets from the waist up. Participants must also not use electronic devices such as cell phones, computers/laptops, MP3 players, etc. during Holter recording. Holter recording will be turned on approximately 30 minutes prior to trial drug administration in each trial period. Participants will not be allowed to shower/bath for the duration of the 24-hour Holter assessment.

Holter data will be extracted (in triplicate) and analyzed by a blinded core ECG laboratory according to a pre-specified algorithm. To minimize artifacts, participants must rest quietly in a semi-recumbent position for ~10 minutes prior to the time points specified for extraction. No other study assessments or procedures should occur during the resting period.

Please see Trial Procedures Manual for Holter-specific procedures provided by the ECG vendor.

Procedures for transfer, archiving, and review of ECGs will be specified by the ECG vendor.

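### In Panels A, B and D a single QTcF of 500 msec or more need not be repeated when baseline is above 440 msec, so the mean that both 500 msec rules rely on may never exist

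*Combined protocol and SAP*

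**What the plan says.** Section 8.3.4 sets the replication of the safety ECGs: "In Panels A, B and D, postdose ECG measurements will be single measurements". Baseline is the mean of a predose triplicate. Panel C has triplicate postdose ECGs.

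The only instruction in 8.3.4 that turns a single postdose reading into three applies "if a participant demonstrates an increase in QTc interval ≥ 60 msec compared with mean predose baseline measurement"; then "the ECG will be repeated twice within 10 minutes", and the mean of the three stands for that time point.

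Two rules act at 500 msec, and both are written on a mean:

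- Section 8.3.4: "If the mean QTc interval is ≥ 500 msec, the Sponsor should be notified". Cardiologist review and telemetry, or consideration of transfer, follow from the same condition.
- Section 8.4.7, item 6 (event of clinical interest): "the average of the three QTcFs will be used".

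Sections 5.1.1 (criterion 4) and 5.1.2 (criterion 12) admit men with QTcF below 450 msec and women with QTcF below 470 msec. Appendix 8 gives looser screening limits (470 and 480 msec) but says that the most conservative criterion applies.

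**The concern.** The repeat trigger is purely relative (a rise of 60 msec), whereas the two rules it feeds are absolute (500 msec). They agree only if everyone who reaches 500 has also risen by 60, and the eligibility limits do not guarantee that. A participant who starts close to the limit can reach 500 msec on a smaller rise. The site then holds one reading, no instruction to take two more, and two rules that need a mean.

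Elsewhere the protocol treats the two thresholds as separate. Appendix 8 lists either one as a potentially significant postrandomization finding. The rule on QT-prolonging co-medication in 8.3.4 uses both: such drugs "should be held until the QTc is within 60 msec of baseline and the QTc is <500 msec". Only the repeat trigger leaves out the 500 msec limb.

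At stake is whether the event-of-clinical-interest report, the prompt Sponsor notification, the cardiologist review and the telemetry happen by rule or by site discretion, in the participants nearest the danger threshold. Safety is the primary objective. Doses go up to 48 mg, there is no data monitoring committee (synopsis), Section 4.4.1 sets no early-termination criteria, and Section 7.1 contains no QTc-specific discontinuation rule. The individual ECG rules therefore carry weight.

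**Working it through.** The plan gives no figure to reproduce here, so the check is threshold arithmetic.

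**Condition for the gap.** Let b be the mean predose baseline and Q a single postdose reading. A repeat is required if Q − b ≥ 60. The gap is Q ≥ 500 with Q − b < 60, that is 500 ≤ Q < b + 60. This range is non-empty only if b + 60 > 500, so only if b > 440.

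**Against the eligibility limits.**

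| | Men | Women |
|---|---|---|
| Baseline limit (msec) | < 450 | < 470 |
| Affected baselines | above 440, below 450 | above 440, below 470 |
| Rise that reaches 500 without a required repeat | more than 500 − 450 = 50, less than 60 | more than 500 − 470 = 30, less than 60 |
| Upper end of uncovered readings | below 450 + 60 = 510 | below 470 + 60 = 530 |

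**At particular baselines.**

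| Baseline | Rise at Q = 500 | Readings of 500 or more with no required repeat |
|---|---|---|
| 440 | 60 | none |
| 441 | 59 | 500 to < 501 |
| 445 | 55 | 500 to < 505 |
| 449 | 51 | 500 to < 509 |
| 460 (women) | 40 | 500 to < 520 |
| 469 (women) | 31 | 500 to < 529 |

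For example, a woman with baseline 469 and a single reading of 528 has risen 528 − 469 = 59 msec. No repeat is required.

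**How many readings the rule governs.**

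- Participants (Tables 2 and 4): 16 + 16 + 20 = 52, of whom 12 + 12 + 12 = 36 on MK-8189.
- Scheduled single dosing-period ECGs per participant, from the footnotes in Section 1.3. Panels A and B share "Day 8, Day 11, Day 14 and Day 17: 8, 10 and 16 hours post-dose", which is 4 × 3 = 12. Panel A adds one on each of Days 2 and 5, giving 14. Panel D has four times on each of five days, 5 × 4 = 20.
- Total: 16 × 14 + 16 × 12 + 20 × 20 = 816. On MK-8189: 12 × (14 + 12 + 20) = 552.

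These are readings under the rule, not expected events.

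**Whether the Holter triplicates fill the gap.** They do not. Section 8.3.4 has them extracted and analyzed by a blinded core laboratory. Dosing-day recordings start on Days 7, 10, 13, 16 and 18 in Panels A and B, against postdose safety ECGs on Days 2 and 5 (Panel A only), 8, 11, 14 and 17. In Panel D they start on Days 1, 4, 7, 10, 13 and 15, against safety-ECG dosing days 2, 5, 8, 11 and 14. One overlap exists: the 24-hour ECG after the Panel D Day 14 dose falls on Day 15, a Holter day. But the Day 15 extractions begin at 2 hours postdose, so they do not supply a mean for that ECG.

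**The case against.** The strongest reply is that the event-of-clinical-interest wording itself implies the repeats. A site with one reading at 500 cannot classify it without three, so it would take two more. On that view this is loose drafting, not a missing safeguard.

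There is also a good deal of surrounding protection:

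- Appendix 8 flags any QTc of 500 msec or more.
- Section 8.3.4 provides for a study cardiologist to be consulted as needed on abnormal tracings.
- A clinically significant ECG change meets the adverse event definition in Appendix 3 and is reported.
- Section 6.6 says "Dose titration decisions for each participant will be based on available (as per the SoA) safety variables", and the 12-lead safety ECG is among them, so the Sponsor sees the readings at each three-day step.
- Participants are confined throughout dosing, and unscheduled safety procedures are allowed.

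Finally, the reach is smaller than 52 participants suggests. Sections 2.1 and 4.2 already cite tolerability up to 24 mg in Panels A and B, so those panels appear largely or wholly dosed. The edit would then act mainly on Panel D: 20 participants, 12 on MK-8189, with 12 × 20 = 240 single ECGs on active drug. Section 4.2.1.1 reports no concentration–QTcF relationship in the earlier multiple-dose study.

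Most of this stands as mitigation. Such a reading would probably be noticed and probably repeated. The reach may well be mainly Panel D, and nothing in the documents shows that the window will be entered, although doses here exceed those studied before. What does not stand is that the gap is closed. In these panels the rise of 60 msec is the only stated route to three postdose safety readings. The Appendix 8 QTc rows name the finding but no action, and the remaining text is discretionary or orders no repeat.

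**Conclusion.** The concern holds. Followed as written, 8.3.4 does not guarantee the mean on which its own 500 msec rule and the event of clinical interest in 8.4.7 depend, for any eligible participant in Panels A, B or D whose baseline QTcF is above 440 msec. The uncovered readings run from 500 to just under 510 msec in men and to just under 530 msec in women. Women have the wider window, and Section 5 aims for approximately 40% women in each panel. Panel C is unaffected.

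This assumes that the predose baseline respects the eligibility limits. A higher baseline would widen the window. Frequency cannot be estimated because the documents give no baseline QTcF distribution; few participants are likely to be affected. No endpoint or estimate changes: the QTc analysis in these panels uses the Holter data. The point should be corrected because it concerns a stated safety trigger for a potentially serious finding, not because many cases are expected.

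**What to change.** In Section 8.3.4, extend the repeat trigger so that the two repeats within 10 minutes follow either a rise of at least 60 msec from the mean predose baseline or any single QTcF of 500 msec or more. Leave the rest of the rule as it is.

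This matches the thresholds in Appendix 8, supplies the three readings that 8.4.7 averages, and reduces the uncovered window to zero at every baseline. It works in both directions: a sustained value reaches the notification and reporting rules, and a noisy single reading is averaged before anyone acts on it as confirmed.

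The cost is one clause, plus two extra ECGs in the rare case concerned, on equipment already in use.
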